9.4.5 BASELINE DESCRIPTIVE STATISTICS

Study groups will be compared on baseline characteristics, including age, race/ethnicity, gender, student group involvement, sexual orientation, and relationship status.

9.4.6 PLANNED INTERIM ANALYSES

Not Applicable

9.4.7 SUB-GROUP ANALYSES

Primary and secondary endpoints will be analyzed based on gender, race/ethnicity, student group involvement, sexual orientation, and relationship status.

9.4.8 TABULATION OF INDIVIDUAL PARTICIPANT DATA

Individual participant data will be listed by measure and time point.

9.4.9 EXPLORATORY ANALYSES

We are not powered to assess outcome measures (sexual violence experiences/behaviors, rape myth acceptance, sexual relationship power); however, exploratory analyses will be performed to assess the direction of effects for our outcome measures to allow for power calculations for future scale-up.

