1 PROTOCOL SUMMARY

1.1 SYNOPSIS

Participant Duration:	For pilot study – 9 months
Title:	MKit: A Pilot Study Testing a Life Skills Application to Address Interpersonal Relationships in College
Study Description:	This study utilizes implementation science principles to culturally adapt a pre-existing web-based application (WebApp) for use with college students. We will use the ADAPT-ITT process to adapt the WebApp to a diverse (race, ethnicity, gender/sexual identity) college population with a focus on life skills and holistic self-care as reinforcement to currently available primary prevention programming available to freshman students. Our hypothesis is that the adapted WebApp will be safe, acceptable, and students will be willing to use it as a reinforcement to current university primary prevention programming.
Objectives:	
• Primary: To evaluate the safety, usability, acceptability, and willingness of using the adapted WebApp among a randomized sample of 300 first year university students.• Secondary: To complete preliminary evaluations on efficacy measures such as sexual victimization/perpetration, rape myth acceptance, and power in sexual relationships to allow for power calculations for a future R-level submission.
Endpoints:	
• Primary: Safety (qualitative interviews), Usability (System Usability Scale, Brooke, 1986), Acceptability (investigator generated), and willingness to use (qualitative interviews).• Secondary: Sexual victimization/perpetration (Sexual Experiences Survey, Koss et al., 2007), Illinois Rape Myth Acceptance – Modified (McMahon & Farmer, 2011), Sexual Relationship Power Scale (Pulerwitz, Gortmaker, & DeJong, 2007)
Study Population:	300 first year university students (150 Control Group, 150 Intervention Group)
Phase:	Pilot
Description of Sites/Facilities Enrolling Participants:	University of Michigan Residence Halls (South and West Quad)
Description of Study Intervention:	Web-based app that uses a life skills approach to address healthy relationships and sexual violence.
Study Duration:	2 years 9 months

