2.2 BACKGROUND

With a national annual incidence rate of 5%, rape is the most frequent violent crime that occurs on college campuses (Finn, 1995; Fisher, Cullen, & Turner, 2000). Nearly 80-90% of college students know the perpetrator, which increases the likelihood that the rape will be completed, rather than attempted (Fisher et al., 2000; Karjane, Fisher, & Cullen, 2005). Furthermore, many college survivors do not perceive or acknowledge their experiences as a rape, often because of lack of evidence, the absence of a weapon, or because alcohol and/or drugs were involved (Fisher, Daigle, Cullen, & Turner, 2003; Karjane et al., 2005). These characteristics of sexual assault in college therefore contribute to the underestimation, under reporting, under prosecution, and low rates of seeking post-assault services among college survivors (BonDurant, 2001; Karjane et al., 2005).

Despite the high prevalence of rape in the United States, an event with long-term negative effects on a survivor's health, few survivors receive comprehensive post-assault care. In the period immediately following a rape, about half of all survivors will have evidence of physical trauma, up to 30% contract a sexually transmitted infection (STI), and 5% of female survivors become pregnant (Resnick et al., 2000). Specific to college survivors, about 20% report physical injuries (Fisher et al., 2000), many fear social consequences so they alienate themselves from campus activities or drop out of school, and it appears that college women who experience post-traumatic stress disorder (PTSD) from an assault may use substances and/or sexual behavior to reduce distress (Messman-Moore, Ward, & Brown, 2009). Post-assault, survivors can access comprehensive health services through referral by rape crisis centers or via the emergency department from specially trained sexual assault nurse examiner (SANE) programs. Comprehensive care includes 1) treatment of physical injuries or other sequelae of the assault, 2) pregnancy prevention including options if emergency contraception is not effective, 3) STI screening and treatment, 4) psychological care for PTSD, 5) forensic and victim services, and 6) legal care including safety from the perpetrator and the ability to report the assault and press

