3 OBJECTIVES AND ENDPOINTS

Objectives	Endpoints	Justification for Endpoints
Primary		
To evaluate the safety, usability, acceptability, and willingness of using the adapted WebApp among a randomized sample of 300 first year university students.	Safety will be assessed through qualitative interviews Usability will be measured through the System Usability Scale (Brooke, 1986)	The endpoints are common outcomes of interest for studies of technological interventions. These outcomes will be measured throughout the study, to observe changes overtime with continued exposure to

	
Acceptability will be measured through an investigator generated scale
 
Willingness to use will be assessed through qualitative interviews
	
the intervention. These endpoints are important outcomes, as interventions must be safe, acceptable, and usable to ensure broad scale uptake.
	
Secondary	
To complete preliminary evaluations on efficacy measures such as sexual victimization/perpetration, rape myth acceptance, and power in sexual relationships to allow for power calculations for a future R-level submission.
	
Sexual victimization/perpetration will be measured using the Sexual Experiences Survey (Koss et al., 2007)
 
Rape myth acceptance will be measured using the Illinois Rape Myth Acceptance – Modified (McMahon & Farmer, 2011)
 
Relationship power differentials will be measured using the Sexual Relationship Power Scale (Pulerwitz, Gortmaker, & DeJong, 2007)
	
The endpoints are important, as the WebApp under study is a primary sexual violence prevention intervention. As such, experiences of sexual violence victimization and perpetration, as well as rape myth acceptance and relationship power (both upstream factors contributing to sexual violence perpetration) are outcomes of interest. Though this pilot study is not powered to detect changes in these secondary outcomes, obtaining data for power calculations for a larger study is a key component of this study.

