Quad) at the University of Michigan will be randomized to receive either: (1) the control arm (n=150) which will receive usual care only (all incoming students receive three programs about healthy relationships and sexual violence including Haven, Relationship Remix, and Change it Up) or (2) the usual care (n=150) described above and the web-based intervention (MKit). We will use cluster-randomization by residence hall (to minimize contamination associated with individual-level randomization of students living in the same residence hall). Following the informed consent process, students in both conditions will complete a baseline survey of 85 questions. Baseline measures will include: 1) demographic data, 2) 20 items from the Sexual Experiences Survey (SES) will measure past experiences with sexual violence (Koss et al., 2007), 3) investigator developed questions on knowledge about sexual violence, 4) 22 items from the modified Illinois Rape Myth Acceptance Scale to measure attitudes endorsing rape myths (McMahon & Farmer, 2011), and 4) 6 items from the Sexual and Relationship Power Scale (SRPS) will measure the multidimensional nature of power in relationships (Pulerwitz & Barker, 2000). All of these are measures have been validated and used extensively in the United States to measure knowledge and attitudes related to gender based violence. Following the survey, students in the Intervention group will be given the opportunity to interact with the application at their own pace, choosing which content to view in the order they prefer.

The Control group will only receive the usual care delivered to all incoming University of Michigan students, which includes Haven (an online course about sexual violence), Relationship Remix (an interactive program about healthy relationships and sexual violence delivered by peers), and Change it Up (a theater based performance on bystander intervention). The Intervention group will receive the usual care described above as well as access to the adapted web-based application. They will be encouraged to interact with the web-based application throughout the study. Data will be collected on the content viewed by the participants, as well as the amount of time they spend within each content area, and the order in which they view the content.

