4.3 JUSTIFICATION FOR DOSE

Intervention group participants will have six months to interact with the WebApp content, as this time period should present sufficient time for meaningful short-term change in the outcomes of interest. Further, the study will run for the duration of the school year, allowing study staff to follow students from the beginning of the school year to the end of the school year as they interact with the WebApp content.

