5.5 STRATEGIES FOR RECRUITMENT AND RETENTION

Students from the target sample, first-year University of Michigan college students, will be recruited for the study. Two residence halls (West Quad and South Quad) at the University of Michigan will be randomized to receive either: (1) the control arm (n=150) which will receive usual care only (all incoming students receive three programs about healthy relationships and sexual violence including Haven, Relationship Remix, and Change it Up) or (2) the usual care (n=150) described above and the web-based intervention (MKit). We will use cluster-randomization by residence hall (to minimize contamination associated with individual-level randomization of students living in the same residence hall). At the end of the Relationship Remix program, a brief announcement will be made about the opportunity to participate in a research study about healthy relationships and palm cards will be distributed (see recruitment materials). We will recruit specifically from Relationship Remix to ensure that all experimental and control subjects receive the same primary prevention programming currently in place on campus. Interested students will receive a palm card with a link to either the MKit web-based application (Intervention) with an access code to sign-up for the website, or a link to the baseline consent and Qualtrics survey (Control) without access to the web-based application. At the end of the study, students from each condition will be invited to participate in an in-person semi-structured interview. Students will receive the invitation to participate in the semi-structured interview on the final page of their 6-month follow-up survey. Students who opt to share their email address with the study team at that time will be contacted to set-up an in-person interview based on user status for the intervention (consistent user of MKit, frequent user of MKit, minimal user of MKit) and a diverse group based on gender, race/ethnicity, and age for the control group. Semi-structured interviews will be conducted with participants from both the Control group (n=10) and the Intervention group (n=15).

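### The direction of the arm difference is named as the input to the future power calculation; a sign cannot serve as one, and with one hall per arm it is confounded with hall

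*Combined protocol and SAP*

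**What the plan says.** The secondary objective is a preliminary evaluation of sexual victimization and perpetration, rape myth acceptance and relationship power, so that a later study can be powered. Section 3 states that "obtaining data for power calculations for a larger study is a key component of this study". Section 9.4.9 gives the means: "exploratory analyses will be performed to assess the direction of effects for our outcome measures to allow for power calculations for future scale-up". Sections 9.4.1 and 9.4.3 each admit that the pilot lacks power for these outcomes and then give direction the same planning role.

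On design, section 5.5 says "Two residence halls (West Quad and South Quad) at the University of Michigan will be randomized to receive either" control or intervention, and section 4.1 says "We will use cluster-randomization by residence hall". That is one hall per arm, with "300 first year university students (150 Control Group, 150 Intervention Group" (synopsis). The arms are compared by ANOVA; no hall term or ICC is mentioned. Section 9.2 reports no formal sample size calculation.

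Sections 9.4.1 and 9.4.3 also plan central tendency, dispersion and frequency distributions at baseline, 3 and 6 months, and all secondary measures are taken in both halls at baseline (section 1.3).

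**The concern.** A power calculation needs a target effect, an SD or an event rate and, if groups are randomised, an ICC. A sign supplies none of these. The sign is also hard to interpret here, because any difference between West Quad and South Quad that arises for other reasons appears as an effect of the app.

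At stake is the secondary objective's usefulness for planning. A team that follows these sections literally carries forward a sign that it cannot use. A team that instead carries forward the difference behind the sign takes a mixture of app effect, hall effect and sampling error. Meanwhile the quantities the pilot can estimate well are not named as planning inputs, and no intervals are requested for them.

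**Working it through.** The plan gives no power, effect size, SD, ICC or expected event figure to reproduce. The check asks how often the observed sign would match the true one.

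**Inputs from the documents**
- 150 students and one hall per arm (synopsis; sections 4.1 and 5.5).
- The only incidence figure, from section 2.2: "With a national annual incidence rate of 5%, rape is the most frequent violent crime that occurs on college campuses". It is national and covers rape only.
- Section 4.3: "Intervention group participants will have six months to interact with the WebApp content"; surveys at baseline, 3 and 6 months.

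**Assumptions, because the documents give no figure:** a six-month window for counting events, no dropout, the effect sizes, the ICCs and any event rate other than 5% per year.

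**1. Expected rape events.** 150 × 0.05 × 0.5 = 3.75 per arm with no app effect (six-month risk 0.025).

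**2. Sign for an event outcome.** Two independent Binomial(150, p) counts, enumerated exactly at ICC 0:

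| Six-month risk, control vs app | Right direction | Tie | Wrong direction |
|---|---|---|---|
| 0.025 vs 0.0125 (halved) | 72% | 13% | 15% |
| 0.025 vs 0.01875 (25% lower) | 57% | 15% | 28% |
| 0.05 vs 0.025 (assumed rate, halved) | 84% | 6% | 9% |
| 0.10 vs 0.05 (assumed rate, halved) | 94% | 2% | 4% |
| 0.10 vs 0.075 (assumed rate, 25% lower) | 75% | 6% | 19% |

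With no effect at risk 0.025, fewer events in the app arm are still seen 43% of the time. Beta-binomial simulation at ICC 0.01 lowers the first row to 65% right and 23% wrong, and the second to 54% and 34%. At risk 0.10 halved, the 94% becomes 84% at ICC 0.01 and 72% at ICC 0.05.

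**3. Sign for a scale score, comparing follow-up only.** With a true effect of 0.2 SD, SE = √[(2/150) × (1 + 149 × ICC)] and P(right sign) = Φ(0.2/SE):
- ICC 0: SE 0.115, 96%
- ICC 0.01: SE 0.182, 86%
- ICC 0.05: SE 0.336, 72%

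**4. Sign for a scale score, comparing change from baseline.** Let r be the within-hall correlation between waves and h the correlation of a hall's own effect between waves. Then Var = 2 × [2(1 − ICC)(1 − r)/150 + 2 × ICC × (1 − h)]. With ICC 0.05 and r = 0.5 (both assumed):
- h = 1 (hall effects fully stable): Var = 2 × 0.00633 = 0.0127, SE 0.113, 96%
- h = 0.5: Var = 2 × (0.00633 + 0.05) = 0.1127, SE 0.336, 72%

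Baseline adjustment therefore helps only as far as hall effects are stable, and two halls cannot show whether they are.

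**5. The ICC.** Two hall means minus two fitted arm means leaves 0 degrees of freedom for between-hall variance at follow-up. Baseline, before the app is used, offers one degree of freedom, too few to be usable. The design effect with 150 per hall is 1 + 149 × 0.01 = 2.49 at ICC 0.01 and 1 + 149 × 0.05 = 8.45 at ICC 0.05, so the missing quantity would matter greatly to a trial that randomises halls.

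**The case against.** The strongest reply is that the plan is open about its limits and already collects much of what is needed. It says repeatedly that it is not powered for these outcomes, and section 8.1 says efficacy is not primary. The dispersion and frequencies it plans are power-calculation inputs, and section 3 speaks of obtaining data, not of direction alone. Baseline is measured in both halls, so a stable hall difference can be seen and subtracted. All of this stands. It does not rescue the sentences at issue: after conceding low power, they still give the planning role to direction, and none of the three sections names the SDs or proportions as the inputs or asks for intervals.

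A reader might infer four stronger things that the documents do not support:

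- **That the direction is close to uninformative throughout.** The 3.75 events apply to rape alone at a national rate. The Sexual Experiences Survey items cover victimization and perpetration more broadly and have no stated rate, so the count may be several times higher. Two of the three outcomes are scale scores, to which no event count applies. Values of 72%, 84%, 94% and 96% are not close to chance.
- **That the secondary objective cannot be met.** The planned descriptive summaries can meet part of it.
- **That a wrong-way result could stop a useful programme.** No progression rule is tied to these outcomes.
- **That the next trial will randomise halls.** The documents speak only of a future submission or scale-up.

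**Conclusion.** Wrong as written, of moderate severity. Sections 9.4.1, 9.4.3 and 9.4.9 name a quantity that cannot feed a power calculation and that, at follow-up, mixes app with hall on all three outcomes.

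How unreliable the sign is depends on the outcome. It is weak for rare events (57% to 72% right for rape at the cited rate, ICC 0, no dropout, six-month window), better for a commoner event (94% for a halving at an assumed 10% per six months), and between 72% and 96% for a 0.2 SD scale effect over assumed ICCs of 0 to 0.05. These percentages rest on assumed effects, rates and ICCs. Two conclusions do not: a sign is not a power input, and one hall per arm yields no usable ICC.

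**What to change.** In 9.4.1, 9.4.3 and 9.4.9, replace direction as the planning input with these quantities, each with a 95% CI:

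- the within-arm SD of each scale and the event proportion at each wave, building on the dispersion and frequencies already planned;
- the correlation between baseline and follow-up, where a participant's waves can be linked;
- the response rate at each wave.

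Present any arm difference as a baseline-adjusted estimate with its CI, labelled as confounded with hall and not to be used as the future target effect. The CI should carry a note that it cannot reflect between-hall variation. State that this pilot cannot supply a hall ICC, so that if the future trial randomises halls the ICC must come from multi-hall data.

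The cost is a change of wording in three sections and a few extra estimates from data already to be collected. The only downside is a more modest claim.

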10 SUPPORTING DOCUMENTATION AND OPERATIONAL CONSIDERATIONS

10.1 REGULATORY, ETHICAL, AND STUDY OVERSIGHT CONSIDERATIONS

10.1.1 INFORMED CONSENT PROCESS

10.1.1.1 CONSENT/ASSENT AND OTHER INFORMATIONAL DOCUMENTS PROVIDED TO PARTICIPANTS

Consent forms describing in detail the study intervention, study procedures, and risks are given to the participant and electronic documentation of informed consent is required prior to starting intervention/administering study intervention. The following consent materials are submitted with this protocol:

- Pilot Control Group Consent Form
- Pilot Intervention Group Consent Form
- Semi-Structured Interview Consent Form

10.1.1.2 CONSENT PROCEDURES AND DOCUMENTATION

Informed consent is a process that is initiated prior to the individual's agreeing to participate in the study and continues throughout the individual's study participation. Consent forms will be Institutional Review Board (IRB)-approved and the participant will be asked to read and review the document. For the pilot study, participants will read through the consent online prior to completion of the baseline survey and make the determination to participate in the study individually. The participant will sign the informed consent document prior to any study activities. Participants will be informed that participation is voluntary and that they may withdraw from the study at any time, and that the study is not connected to their schooling.

For the semi-structured interview, the investigator will explain the research study to the participant and answer any questions that may arise. A verbal explanation will be provided in terms suited to the participant's comprehension of the purposes, procedures, and potential risks of the study and of their rights as research participants. Participants will have the opportunity to carefully review the written consent form and ask questions prior to signing. The participant will sign the informed consent document prior to any study activities. Participants will be informed that participation is voluntary and that they may withdraw from the study at any time, and that the study is not connected to their schooling. A copy of the informed consent document will be offered to the participants if they would like it. The informed consent process will be conducted and documented in the source document (including the date), and the form signed, before the participant undergoes any study-specific procedures.

10.1.2 STUDY DISCONTINUATION AND CLOSURE

This study may be temporarily suspended or prematurely terminated if there is sufficient reasonable cause. Written notification, documenting the reason for study suspension or termination, will be provided by the suspending or terminating party to study participants, funding agencies, and regulatory authorities. If the study is prematurely terminated or suspended, the Principal Investigator will promptly inform study participants, the Institutional Review Board (IRB), and sponsor and will provide the reason(s) for the termination or suspension. Study participants will be contacted, as applicable, and be informed of changes to study visit schedule.

Circumstances that may warrant termination or suspension include, but are not limited to:

- Determination of unexpected, significant, or unacceptable risk to participants
- Insufficient compliance to protocol requirements
- Data that are not sufficiently complete and/or evaluable
- Determination that the primary endpoint has been met
- Determination of futility

Study may resume once concerns about safety, protocol compliance, and data quality are addressed, and satisfy the sponsor and/or IRB.

